Treatment compliance of each study subject will be calculated and summary statistics of compliance per treatment group will be presented.
- The Basic Information on Study Subject (Your Basic Profile)
Frequency of answers to each question at each visit will be analyzed per treatment group.

CONFIDENTIAL

Rationale for the number of planned study subjects:

In this clinical study, to discuss the changes in the total score for all questions in the DTR-QOL Questionnaire from the baseline (Week 0) to the end of the treatment period, as the primary endpoint, mean changes in the daily DPP-4 inhibitor and trelagliptin groups were assumed as 14.4% and 19.0%, respectively. The mean change in the daily DPP-4 inhibitor group was assumed by reference to the data on a sodium glucose transporter 2 (SGLT2) inhibitor, from the previous research; and that in trelagliptin group was assumed by reference to the data from the validation trial of the DTR-QOL Questionnaire. The common SD was assumed as 12.1 % considering the former assumption. When 5% of significance level (two-sided) is based for the analysis of the primary endpoint, 110 subjects per group would be needed to ensure 80% power in comparisons between the trelagliptin group and daily DPP-4 inhibitor group. As this is a study on treatment for type 2 diabetes with DPP-4 inhibitors currently used in the medical setting, the number of randomized subjects was established as 120 subjects per group, for a total of 240 subjects, assuming a type 2 diabetes treatment discontinuation rate of 8%*.

*Based on the results for Topic 2 of the “Strategic Studies on the Prevention of Diabetes” (JDOIT-2), the annual discontinuation rate for the “usual care group” without intervention is approximately 8%.

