8.5 Preparation and storage of allocation list

The allocation responsible person (designated by the sponsor) shall create an allocation list.

Study subjects will be allocated at the Case Registration Center through the Case Registration Web System, using "the total score for the DTR-QOL Questionnaire [$<80\% (<168.2 \text{ as a score})$ or $\geq 80\% (\geq 168.2 \text{ as a score}^{\text{※}})$]" and "HbA1c ($<8.0\%$ or $\geq 8.0\%$)" at the start of the screening period as stratification factors. The Case Registration Center will use the allocation list for stratification prepared by the allocation responsible person in operating the treatment allocation.

※ Refer to the section 9.1.9 for the calculation method of the total score for the DTR-QOL Questionnaire.

Information on the allocation shall be kept in a safe place and shall not be available to anyone other than authorized persons, to secure independency from the clinical research.

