 - 3) The analyses below carried out on the total score for each factor provided through the DTR-QOL Questionnaire, and on the total score for treatment satisfaction in the DTSQ: A comparison between the treatment groups will be carried out based on the ANCOVA model using "the change in the total score by the end of treatment [the end of the treatment period (Week 12) - baseline (Week 0)]" as a dependent variable; the total score at the baseline (Week 0), the total score of "the DTR-QOL Questionnaire (<80% or \geq 80%)" at the baseline (Week 0) and "HbA1c (<8.0% or \geq 8.0%)" at the baseline (Week 0) as covariates; and "a treatment group" as an independent variable. The level of significance will be 5% (two-sided). Note that the total score for all questions in the DTR-QOL is out of the scope of the analysis.
 - 4) To indicate the changes in the total scores for all questions in the DTR-QOL Questionnaire and the total scores for treatment satisfaction in the DTSQ, the summary statistics and two-sided 95% CI for means per treatment group will be calculated, with stratification by the following factors at the start of the treatment period (Week 0):
 - Use of medication for treatment of comorbidities
 - Number of daily doses of medication for treatment of comorbidities (<2 times or \geq 2 times)

- Total number of daily tablets of medication for treatment of comorbidities (<2 tablets or ≥ 2 tablets)
- Number of doses of the study drug or comparative drug (once weekly, once daily or twice daily)
- Changes in the scores per question in the DTR-QOL Questionnaire at each assessment time point.
- Changes in the scores for per question in the DTSQ at each assessment time point.
 - 1) Summary statistics for measurements and the changes from the baseline (Week 0) will be calculated per treatment group.

<Other endpoints>

Summarizations below will be performed in the "full analysis set" (FAS).

- Laboratory tests
Treatment compliance of each study subject will be calculated and summary statistics of compliance per treatment group will be presented.
- Treatment compliance
Treatment compliance of each study subject will be calculated and summary statistics of compliance per treatment group will be presented.
- The Basic Information on Study Subject (Your Basic Profile)
Frequency of answers to each question at each visit will be analyzed per treatment group.

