13.3 Determination of the number of planned study subject

In this clinical study, to discuss changes in the total score for all questions in the DTR-QOL Questionnaire from the baseline (Week 0) to the end of the treatment period, as the primary endpoint, mean changes in the daily DPP-4 inhibitor and trelagliptin groups were assumed as 14.4% and

CONFIDENTIAL

19.0%, respectively. The mean change in the daily DPP-4 inhibitor group was assumed by reference to the data on SGLT2 inhibitor, from the previous research ⁴⁾; and that in trelagliptin group was assumed by reference to the data from the validation trial of the DTR-QOL Questionnaire ⁶⁾. The common SD was assumed as 12.1 % considering the former assumption. When 5% of significance level (two-sided) is based for the analysis of the primary endpoint, 110 subjects per group would be needed to ensure 80% power in comparisons between the trelagliptin group and daily DPP-4 inhibitor group. As this is a study on treatment for type 2 diabetes with DPP-4 inhibitors currently used in the medical setting, the number of randomized subjects was established as 120 subjects per group, for a total of 240 subjects, assuming a type 2 diabetes treatment discontinuation rate of 8%*.

*Based on the results for Topic 2 of the “Strategic Studies on the Prevention of Diabetes” (JDOIT-2), the annual discontinuation rate for the “usual care group” without intervention is approximately 8%²⁾.

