2 EFFICACY EVALUATIONS

2.1 Primary Endpoint and the Analytical Methods

Analysis Set: Full Analysis Set

Items: Change from Baseline in DTR-QOL Total Score at End of Study (Week 12)

Method: Analysis of covariance (ANCOVA) is conducted to compare between the treatment groups using "Change from baseline in DTR-QOL total score by the end of treatment [the End of Study (Week 12) - baseline (Week 0)]" as a dependent variable; DTR-QOL Total Score at the start of the screening period(<80 or ≥ 80) and HbA1c ($<8.0\%$ or $\geq 8.0\%$) at the start of the screening period as covariates; and "treatment group" as an independent variable. The level of significance is defined as 5% (two-sided).

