2.2 Secondary Endpoints and the Analytical Methods

Analysis Set: Full Analysis Set

Items: 1) DTR -QOL Total Score
2) DTR -QOL Total Score of Factor1 to Factor 4
"Factor 1: Burden on Social Activities and Daily Activities" (13 questions)
"Factor 2: Anxiety and Dissatisfaction with Treatment" (8 questions)
"Factor 3: Hypoglycemia" (4 questions)
"Factor 4: Satisfaction with Treatment" (4 questions)
3) DTSQ Total Score
4) DTR -QOL Total Score of Each Items
5) DTSQ Total Score of Each Items

Analysis Visit: Week 0, Week 4, Week 12, End of Study

Method:

- (1) The following analysis will be performed for the Items 1 to 3 described above.
 Summary statistics of observed value and 95% confidence interval for the mean will be calculated by treatment groups and Analysis Visit. In addition, Mean (+/-SD) plots will be made by treatment group and Analysis Visit. Adjusted mean differences and the 95% confidence interval (two-sided) will also be provided. The same analyses described above will be performed on change from baseline at each analysis visit.
- (2) The following analysis will be performed for the Items 2 to 3 described above.
 Analysis of covariance (ANCOVA) will be conducted to compare between the treatment groups using "the change from baseline in the total score by the end of treatment [the End of Study(Week 12) - baseline (Week 0)]" as a dependent variable; the total score of "the DTR-QOL Total score (<80 or ≥ 80)" at the baseline (Week 0) and "HbA1c (<8.0% or $\geq 8.0\%$)" at the baseline (Week 0) as covariates; and "a treatment group" as an independent variable.
- (3) The following analysis will be performed for the Items 1, 3 described above.
 The summary statistics and two-sided 95% CI for means of change from baseline by treatment group will be calculated, with stratification by the following factors at the start of the treatment period (Week 0):
 - Use of medication for treatment of comorbidities;
 - Number of daily doses of medication for treatment of comorbidities (<2 times or ≥ 2 times);
 - total number of daily tablets of medication for treatment of comorbidities (<2 tablets or ≥ 2 tablets);
 - Number of doses of the study drug or comparative drug (once weekly, once daily or twice daily).
- (4) The following analysis will be performed for the Items 4 -5 described above.
 Summary statistics for measurements and the change from baseline (Week 0) will be calculated by treatment group per question at each analysis visit.

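### SAP 2.2(2) omits each secondary outcome's own Week 0 score, which the protocol requires, and so loses precision; its Week 0 categories also do not match the randomisation strata

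*SAP*

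**What the plan says.** **Randomisation.** Protocol 8.5 allocates by DTR-QOL total (below 80%, or 80% and above) and HbA1c (below 8.0%, or 8.0% and above), both taken "at the start of the screening period as stratification factors".

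**Primary model.** Protocol 13.1.3 adjusts for the continuous Week 0 total and the two screening categories. SAP 2.1 lists only the two categories, "at the start of the screening period as covariates"; the continuous Week 0 total is absent.

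**Secondary models (Factors 1 to 4 and the DTSQ total).** Protocol 13.1.3, secondary item 3), begins its covariates with "the total score at the baseline (Week 0), the total score of" the DTR-QOL category, so the outcome's own Week 0 score is a covariate in its own right. The two categories are then taken at Week 0. The protocol summary says the same, and so do both protocol texts in the file, so the SAP is not following a superseded version. SAP 2.2, Method (2), has only the two categories "at the baseline (Week 0) as covariates; and" treatment group.

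SAP 2.4.1 refers back to 2.1 and 2.2 and adds no covariate. The SAP revision history gives no reason for the difference.

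**The concern.** Two separate things differ here, and they have different consequences.

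1. **The own Week 0 score is missing from the SAP.** Protocol 13.1 leaves the detailed methods to the SAP, so an analyst following the SAP would run five tests that the protocol does not describe. A change in Factor 3 or in the DTSQ would be adjusted only for a split of a different score and a split of HbA1c. Change scores carry regression to the mean: with equal variances, a chance baseline difference d between arms moves the unadjusted estimate by about -(1 - rho)d, where rho is the correlation between Week 0 and Week 12. The own baseline removes this shift and the variance that goes with it; a split of another score removes only part.

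2. **The categories are re-formed at Week 0 in both documents.** These are not the groups within which subjects were allocated, and the primary model in both documents uses the screening groups. A Week 0 DTR-QOL total or HbA1c that is missing also removes a subject from the model under SAP 2.4.2, even when the outcome itself is complete. The screening values are needed for entry and allocation, so they should be available for everyone randomised.

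**Working it through.** **The plan's own figure.** Protocol 13.3 and the summary give: "mean changes in the daily DPP-4 inhibitor and trelagliptin groups were assumed as 14.4% and 19.0%, respectively"; "The common SD was assumed as 12.1 % considering the former assumption"; two-sided 5%; "110 subjects per group would be needed to ensure 80% power".

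- Difference: 19.0 - 14.4 = 4.6.
- Normal approximation: n = 2 x (1.960 + 0.842)^2 x 12.1^2 / 4.6^2 = 108.6, so 109 per group. The exact two-sample t calculation gives 109.6, so 110.
- Discontinuation of 8%: 110 / 0.92 = 119.6, so 120.

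The stated 110 and 120 reproduce. They concern the primary endpoint and assume no gain from baseline adjustment. No SD, effect or power is stated for the secondary ANCOVAs, so what follows is in relative terms.

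**Cost of omitting the own baseline, no categories in the model.** With equal SD s at both visits:

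- variance of the change: 2s^2(1 - rho)
- residual variance with the own baseline as covariate: s^2(1 - rho^2)
- ratio: 2 / (1 + rho)

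**With the categories in the model.** A simulation of 400,000 subjects per scenario compared the SAP model (Week 0 categories only) with own baseline plus screening strata. Assumptions, none of them in the documents: normal scores; correlation of the outcome's baseline with the DTR-QOL total 0.3, 0.6 or 0.85; 20% or 50% of subjects at or above 80; screening to Week 0 correlation 0.8 for DTR-QOL and 0.9 for HbA1c; HbA1c unrelated to the outcome. The last column is the power under the SAP model of a comparison that would have 80% with the corrected model: Phi(2.802 / sqrt(ratio) - 1.960).

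| rho | 2/(1+rho) | SAP model / corrected model | Power, SAP model |
|---|---|---|---|
| 0.3 | 1.54 | 1.29-1.52 | 62-69% |
| 0.5 | 1.33 | 1.18-1.32 | 69-73% |
| 0.7 | 1.18 | 1.09-1.17 | 74-76% |
| 0.8 | 1.11 | 1.06-1.11 | 76-78% |

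Worked example: ratio 1.318 gives 2.802 / 1.148 - 1.960 = 0.481, and Phi(0.481) = 0.685. In subjects, at rho 0.5 the 110 evaluable per group do the work of about 83 (110 / 1.32) to 93 (110 / 1.18).

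**Cost of the category timing alone.**

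- *Own baseline in the model.* Replacing Week 0 categories with screening strata leaves the variance unchanged (ratio 1.00) when the screening score predicts Week 12 only through Week 0. As a second case, I used the DTR-QOL total as its own outcome, with all visit correlations equal at 0.45 to 0.8, mean 65 or 75 and change SD 12.1. There the Week 0 version has 3 to 8% more variance.
- *Categories only.* The direction reverses. The screening version has 0 to 7% more variance in the first set of scenarios and 5 to 20% more in the second.

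The loss in the table therefore comes from the missing baseline score.

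**The case against.** The Week 0 categories are prespecified and stated consistently in the protocol summary, protocol 13.1.3 and SAP 2.2. The SAP's time windows place them before Day 1, so they are meant to be pre-treatment covariates. The secondary tests have no stated power and, under SAP 2.4.5, no multiplicity adjustment. All of this stands. It limits the timing point to a question of alignment.

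A reader might go further in four ways that the documents do not support.

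- *That the Week 0 categories bias the secondary comparisons.* Adjusting for a covariate measured before treatment does not by itself bias the comparison, and nothing in either document shows that it does here.
- *That the Week 0 categories cause the loss of precision.* They do not. Switching to screening strata without adding the baseline score would make the SAP model slightly worse.
- *That Week 0 answers may be given after the arm is known, which favours the screening strata.* Protocol 9.2.2 puts the questionnaires and randomisation at the same visit without stating their order, and the trial is open-label. But the Week 0 score enters every change score and would remain as a covariate, so changing the strata would not remove such an effect. HbA1c is a laboratory value, not a subject's answer. The order of events at Visit 2 is a separate matter.
- *That the SAP's secondary models depart from its primary model on the baseline score.* SAP 2.1 leaves that score out as well. On this point both SAP models depart from the protocol; only the category timing separates SAP 2.2 from SAP 2.1.

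What the objection does not answer is the omission itself: the protocol names the own Week 0 score, and the SAP does not.

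**Conclusion.** The point holds in two parts of unequal weight.

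The main part is a contradiction between protocol and SAP that reduces precision in all five secondary ANCOVAs. The size depends on correlations that the documents do not give. Over rho 0.3 to 0.8, the SAP model's variance is roughly 5 to 50% higher (6 to 52% in the scenarios run). The range assumes normal scores, equal variances at Week 0 and Week 12, and the links between scores listed above; it is an illustration, not an estimate for any one factor or for the DTSQ.

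The lesser part is that both documents use Week 0 categories where the design and the primary model use screening strata. This is a mismatch, with no bias shown and a precision cost of 0 to about 8% once the own baseline is included.

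The change to SAP 2.2 touches secondary endpoints only, and the stated sample size is unaffected. It should be made, but the trial does not depend on it.

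**What to change.** 1. **SAP 2.2, Method (2):** add as a covariate the continuous Week 0 score of the outcome being analysed (that factor's score, or the DTSQ total). Replace the Week 0 categories with the screening (Week -4) DTR-QOL and HbA1c strata. Make both changes together; do not swap the categories without adding the score.
2. **Protocol 13.1.3, secondary item 3), and the protocol summary:** change the two categories from Week 0 to screening. The own-baseline covariate is already there.
3. **SAP 2.1:** restore the continuous Week 0 DTR-QOL total, as protocol 13.1.3 specifies for the primary analysis. If only 2.2 were corrected, the SAP's secondary models would be baseline-adjusted and its primary model would not.

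The cost is wording in the SAP and protocol and the matching change to the analysis programs. Every value needed is already collected.

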2.3 Other Analysis

Analysis Set: Full Analysis Set

Items:

- 1) Laboratory Tests

Serum Chemistry:

HbA1c
 Fasting Blood Glucose
 Fasting Insulin
 Fasting Glucagon
 Fasting Glycoalbumin
 1.5 -AG
 Serum creatinine

Urinalysis:

Urinary 8-OHdG (using a correction value of uric creatinine)
 Urinary creatinine

2) Treatment Compliance

3) The Basic Information on Study Subject

How was Blood Glucose level in [1: Well-Controlled, 2, 3: Not Sure, 4, the previous a month? 5: Poorly-Controlled]
 Which diabetes Med do you like [3 Times Daily, Twice Daily, Once to use? If efficacy, side effect, Daily, Once a Week, Any Will be cost are equivalent OK]
 Have you experienced [Yes, No] hypoglycemia in the previous a month?
 How many times have you [0, 1, 2, 3, 4, 5<= - <=Max] experienced hypoglycemia in the previous a month?
 When do you take other medicine [Breakfast, Lunch, Dinner, Bedtime, (ex. hyperpiesia) in the previous a month? No Rules, Not Taking]
 [multiple answers are allowed]
 How often do you forget to take [Never, Rarely, 1-3 Times per Month, other medicine (ex. hyperpiesia) Once a Week, A Few Times a Week, in the previous a month? >4 Times a Week, Not Taking]
 What kind Job are you with? [Full Time Job, Part Time Job, No Job, Other]
 How many Days Go to Work or [Rarely, 1-2 Days per Week, 3-4 Days go outside from Morning? per Week, 5-6 Days per Week, 7 Days per Week]

Hours taken from wake up to leave Home	[Less than 1 hr, More than 1 hr Less than 2 hr, More than 2 hr Less than 3 hr, More than 3 hr]
How often do you have to take medicine during busy hours in the previous one month ?	[Always, Sometimes, Occasionally, Rarely, Never]
When do you take diabetes medicine? [multiple]	[Breakfast, Lunch, Dinner, Bedtime, No Rules, Not Taking]
How Often do you forget to take diabetes medicine in the previous one month ?	[Never, Rarely, 1-3 Times per Month, Once a Week, A Few Times a Week, >4 Times a Week, Not Taking,]
Felt guilty when forgot to take DM medicine	[Exactly, Somewhat, Not Sure, Not Exactly, Never]
Burdensome to take diabetes medicine outside	[Exactly, Somewhat, Not Sure, Not Exactly, Never]
Analysis Visit:	Item 1: Week 0, Week 4, Week 12, End of Study Item 3: Week 0, Week 4, Week 12, End of Study
Method:	
(1) The following analysis will be performed for the Items 1 described above.
 
Summary statistics of observed value and change from baseline (week 0) will be calculated by treatment groups. Mean differences and the 95% confidence interval (two-sided) will also be provided. In addition, Mean (+/-SD) plots will be made by treatment group.
 
(2) The following analysis will be performed for the Items 2 described above.
 
Treatment compliance of each subject will be calculated and summary statistics of compliance by treatment group will also be provided.
 
(3) The following analysis will be performed for the Items 3 described above.
 
Frequency distribution to each question will be analyzed by per treatment group.

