 - (3) The analyses below carried out on the total score for each factor provided through the DTR-QOL Questionnaire, and on the total score for treatment satisfaction in the DTSQ: A comparison between the treatment groups will be carried out based on the ANCOVA model using a change in the total score by the end of treatment [the end of the treatment period (Week 12) - baseline (Week 0)] as a dependent variable; the total score at the baseline (Week 0), the total score of “the DTR-QOL Questionnaire (<80% or ≥80%)” at the baseline (Week 0) and “HbA1c (<8.0% or ≥8.0%)” at the baseline (Week 0) as covariates; and a treatment group as an independent variable. The level of significance will

be 5% (two-sided). Note that the total score for all questions in the DTR-QOL is out of the scope of the analysis.

- (4) To indicate the changes in the total scores for all questions in the DTR-QOL Questionnaire and the total score for treatment satisfaction in the DTSQ, the summary statistics and two-sided 95% CI for means per treatment group will be calculated, with stratification by the following factors at the start of the treatment period (Week 0):
 - Use of medication for treatment of comorbidities
 - Number of daily doses of medication for treatment of comorbidities (<2 times or \geq 2 times)
 - Total number of daily tablets of medication for treatment of comorbidities (<2 tablets or \geq 2 tablets)
 - Number of doses of the study drug or comparative drug (once weekly, once daily or twice daily)
- Changes in the scores per question in the DTR-QOL Questionnaire at each assessment time point.
- Changes in the scores for per question in the DTSQ at each assessment time point.
 - (1) Summary statistics for measurements and the changes from the baseline (Week 0) will be calculated per treatment group.

Safety endpoints:

Frequency tables will be prepared for the incidences of adverse events, hypoglycemia, and hospitalization (duration and number) for type 2 diabetes after the first administration of the study drug or comparative drug in the “safety population” in each treatment group.

<Other Endpoints>

Summarizations below will be performed in the "full analysis set" (FAS).

- Laboratory tests
Summary statistics for measurements and the changes from the baseline (Week 0) will be calculated per treatment group to plot the changes in means and SDs.
- Treatment compliance

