6.2 Rationale for the clinical study design

(1) Rationale for the clinical study design

The study was designed as an open-label, parallel-group comparative study, to assess impact of trelagliptin on QOL of type 2 diabetes compared with Daily DPP-4 inhibitors. In conducting this parallel-group comparative study, randomization with stratification will be performed, using "the total score for all factors (1-4) in the DTR-QOL Questionnaire (<80% or ≥80%)" and "HbA1c (<8.0% or ≥8.0%)" as stratification factors, for the purpose of adjusting effects on the reduction level of diabetes treatment burdens in patients controlled by diet/exercise therapy during Visit 1.

(2) Rationale for the study period

The treatment period was designed as 12 weeks, because switch to other treatment including combination therapy with other medications is recommended for a case fails to achieve the therapeutic target following three-month continuous administration, as the evaluation on responses to treatment with oral diabetic medications¹⁾, and in a study which investigate changes in DTR-QOL score during treatment with sodium glucose transporter 2 (SGLT2) inhibitor, statistically significant increase in the score was observed at 12 weeks of treatment and scores at 12 weeks and 24 weeks was comparable.

(3) Rationale for the number of planned study subjects

See Section 13.3.

6.3 Premature termination of entire clinical study or premature termination of clinical study at a study site

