2.4 CONSIDERATIONS on STATISTICAL ANALYSIS

2.4.1 Adjustments for Covariates

ANCOVA will be performed on primary and secondary endpoints using treatment group as independent variables. Details are described in 2.1 and 2.2

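### SAP 2.3 plans unadjusted between-arm laboratory differences without saying which quantity they apply to; an ANCOVA on the Week 0 value would give one narrower estimate per item and visit (minor)

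*SAP*

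**What the plan says.** SAP 2.3 lists nine laboratory items: HbA1c, fasting glucose, insulin, glucagon, glycoalbumin, 1,5-AG, serum creatinine, urinary 8-OHdG and urinary creatinine. The visits are "Item 1: Week 0, Week 4, Week 12, End of Study". Method (1) has two steps. The first is descriptive: "Summary statistics of observed value and change from baseline (week 0) will be calculated by treatment groups". The second compares the arms: "Mean differences and the 95% confidence interval (two-sided) will also be provided". No model, covariate or outcome quantity is given for the second step.

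Two other places in the SAP indicate that this difference is unadjusted. For the questionnaire scores, SAP 2.2 Method (1) uses a different term: "Adjusted mean differences and the 95% confidence interval (two-sided) will also be provided". SAP 2.4.1 sets the reach of covariate adjustment: "ANCOVA will be performed on primary and secondary endpoints using treatment group as independent variables". Laboratory tests are neither primary nor secondary endpoints.

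The protocol does not fill the gap. Section 5.2.3 puts laboratory tests under Other Endpoints, and the Study Summary plans only group-wise description and plots: "Summary statistics for measurements and the changes from the baseline (Week 0) will be calculated per treatment group". The laboratory entry in section 13.1.3 repeats the treatment-compliance text. The between-arm interval is therefore the SAP's own addition.

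Protocol 8.5 allocates by DTR-QOL total score and HbA1c (below 8.0%, or 8.0% and above) "at the start of the screening period as stratification factors". The HbA1c stratum is thus a Week -4 value, separate from the Week 0 measurement.

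**The concern.** Each item is measured at Week 0, and for HbA1c the randomisation stratum is also known, yet the planned between-arm interval uses this information only partly or not at all. Two consequences follow.

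- **Precision.** A raw difference in observed values leaves in all the between-subject variation that Week 0 could explain. A raw difference in change subtracts the Week 0 value with a fixed coefficient of 1, which is less efficient than estimating the coefficient.
- **Ambiguity.** If differences are produced for both quantities, every item and post-baseline visit has two unadjusted estimates, with nothing to say which is to be read. With nine items and three post-baseline analysis visits (Week 4, Week 12, End of Study), that is 9 × 3 × 2 = 54 differences.

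What is at stake is the precision and clarity of supporting laboratory comparisons. The primary analysis is not touched.

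**Working it through.** **Inputs from the documents.** Protocol 13.3: assumed mean changes 14.4 and 19.0 (difference 4.6), SD 12.1, two-sided 5%, 80% power, 110 evaluable and 120 randomised per group, 8% discontinuation. The documents give no precision target for any laboratory item.

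**The plan's own figure.** The normal approximation gives 2 × (1.960 + 0.842)² × (12.1/4.6)² = 108.6, so 109 per group. The noncentral-t version gives 110 (power 80.1%). Then 110/0.92 = 119.6, so 120. The stated sizes reproduce, and n = 110 per arm is used below.

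**Assumptions not in the documents.** The SD is the same at Week 0 and Week 12. The correlation r between the two visits is 0.5 to 0.9, with 0.3 shown as a further check.

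**Variance of the between-arm difference**, as a multiple of 2σ²/n:

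- observed value: 1
- change from Week 0: 2(1 − r)
- ANCOVA on the Week 0 value: 1 − r²

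The ANCOVA variance is therefore (1 + r)/2 of the change-score variance and 1 − r² of the observed-value variance. The excess width is 1/√ratio − 1. In SD units, the 95% half-width is 1.96 × √(2/110) = 0.264 times the square root of the multiple.

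| r | Observed | Change | ANCOVA | Observed wider by | Change wider by |
|---|---|---|---|---|---|
| 0.3 | 0.264 | 0.313 | 0.252 | 5% | 24% |
| 0.5 | 0.264 | 0.264 | 0.229 | 15% | 15% |
| 0.7 | 0.264 | 0.205 | 0.189 | 40% | 8% |
| 0.8 | 0.264 | 0.167 | 0.159 | 67% | 5% |
| 0.9 | 0.264 | 0.118 | 0.115 | 129% | 3% |

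**Gap between the two raw estimates.** Write Y for the post-baseline value and X for the Week 0 value, with bars for arm means among subjects who have both. Then (Ȳ₁ − Ȳ₂) − [(Ȳ₁ − X̄₁) − (Ȳ₂ − X̄₂)] = X̄₁ − X̄₂, the chance Week 0 imbalance. Under simple randomisation its SE is √(2/110) = 0.135 SD, a 95% range of about ±0.26 SD. It is smaller for HbA1c because allocation is stratified on the screening value.

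**Simulation for an HbA1c-type item.** Settings, all assumed: 3,000 trials per setting, 220 subjects, no true effect, normal data, permuted blocks of 4, about 27% of subjects above the stratum cut, screening-to-Week 0 correlation 0.9, and r from 0.5 to 0.9. The ANCOVA contained the Week 0 value and the stratum.

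- Coverage of nominal 95% intervals: observed value 96.7% to 99.0%, change 95.1% to 96.3%, ANCOVA 94.7% to 95.5%. The simulation error is about √(0.95 × 0.05/3000) = 0.4 percentage points.
- The two raw estimates had opposite signs in 26% to 38% of trials.

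**The case against.** The strongest reply is that the SAP treats these items as the protocol ranks them. They are Other Endpoints, the Study Summary asks only for description, SAP 2.4.1 confines ANCOVA to primary and secondary endpoints, SAP 2.3 specifies no laboratory p-value, and no power claim rests on them. Randomisation keeps both raw differences unbiased, and ignoring the stratum makes the intervals conservative, not too narrow. If the difference is taken on change and r is high, the loss is only a few per cent. The correlation and the equal SDs are assumptions, and treatment may alter the spread of HbA1c. The contrast with SAP 2.2 is also imperfect: its Method (1) names no covariates for its adjusted difference, and the ANCOVAs written out in SAP 2.1 and 2.2 list no Week 0 score of the outcome. All of this stands, and it limits the weight of the point. It does not supply the missing definition of the difference or a reason to leave the Week 0 value unused.

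A reader might also infer more than the documents support:

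- **That every laboratory difference ignores Week 0.** This is true only of the observed-value difference.
- **That two competing estimates will certainly be reported.** This is the natural reading of Method (1), but it is not stated. SAP 2.2 Method (1) expressly repeats its analyses on change; SAP 2.3 does not.
- **That the HbA1c difference is the main supporting comparison for the quality-of-life result.** Neither document says so. Protocol 5.1 states the objective as reduction in treatment burden.
- **That both randomisation strata belong in all nine models.** Protocol 6.2 gives their purpose as "as stratification factors, for the purpose of adjusting effects on the reduction level of diabetes treatment burdens". Nothing in the documents shows a gain for the eight items other than HbA1c beyond their own Week 0 value.

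**Conclusion.** The point holds as a minor one. The laboratory differences are planned without covariate adjustment and without a stated outcome quantity. They are unbiased, and their intervals are valid to conservative. The cost is excess width: 15% down to 3% for change and 15% up to 129% for observed values as r goes from 0.5 to 0.9. If both quantities are reported, the cost includes disagreement equal to the Week 0 imbalance among subjects with both values. The large percentages apply only if the observed-value difference is the one reported and r is high.

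The sizes rest on equal SDs and the assumed r. The coverage and sign results rest further on the simulation settings. That the differences are unadjusted and the quantity undefined rests on the SAP text alone. No wrong conclusion about the primary endpoint follows.

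**What to change.** In SAP 2.3 Method (1), define one between-arm estimate per item and post-baseline visit: an ANCOVA of change from Week 0 on treatment group and the Week 0 value of the same item, reported as an adjusted difference with its 95% CI. With the Week 0 value in the model, the treatment estimate is the same whether the outcome is the change or the observed value, so the ambiguity disappears. For HbA1c, add the screening HbA1c stratum. For the other eight items the strata are optional. Keep the raw group summaries and plots as description.

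The cost is SAP wording and a little programming, with no new data. There is one downside: subjects without an accepted Week 0 value drop out of the model. The SAP Time Window tables accept HbA1c at Week 0 over study days -14 to -1 but the other laboratory items on day -1 only, so the loss could matter for those items. It is a loss relative to the observed-value difference only, since a change score needs the Week 0 value too. Report the number analysed for each item.
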